The use of human subjects is proposed in this application. Informed consent will be obtained from each subject prior to any study related procedures. After informed consent has been obtained, potential subjects will be screened to ensure they meet diagnostic and safety criteria for inclusion in the study. Subjects will then be randomly assigned via a randomization list to one of three doses (2.5mg/ml versus 5mg/ml versus 10mg/ml) of IL TAC or placebo (intralesional saline) in a 1:1:1:1 ratio. Bacteriostatic saline is chosen as a diluent and placebo instead of xylocaine as the injection stings less. The concentration, frequency of injection of the study medication and diluents used are determined based on current standard of care in clinical practice for the treatment of patients with alopecia areata. Therefore, patients being treated with IL TAC 2.5mg/ml will have up to a maximum of 12ml of drug injected, those treated with IL TAC 5mg/ml will have up to a maximum of 6ml of drug injected, while patients being treated with IL TAC 10mg/ml will receive a maximum of up to 3ml of drug injected. In an attempt to maintain the blinding of the evaluating investigator, patients receiving saline placebo, will have either 3ml, 6ml, or 12ml drawn up drawn up as appropriate for the extent of hair loss present and at the discretion of the unblinded study staff member preparing the medication. The entire syringe will be covered. After injections are completed, the unblinded study team member will collect the used and unused syringes and calculate the total volume injected. This amount will be recorded and concealed to maintain integrity. During the course of the study, subjects will be closely monitored for efficacy and the occurrence of adverse events. Determination of immunologic outcome measures will require the collection of blood samples (peripheral blood draws) as well as skin biopsies from the scalp. The subject population will consist of 68 patients with a diagnosis of patchy AA of recent onset (duration of at least 3 months) who have consented to participation in the trial and have met all inclusion and exclusion criteria. Patients will be 18 to 75 years old, and be deemed to be in good general health. We do not intend to enroll patients from vulnerable populations.

Inclusion criteria

- Patients 18 to 75 years of age
- Patients with a diagnosis of patch type alopecia areata

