- Patients will have up to 50% total scalp hair loss at baseline as measured by the Severity of Alopecia Tool (SALT) (2) score.
- Duration of hair loss greater than 3 months without an upper limit of duration as long as there is reason to believe that regrowth is possible in the opinion of the investigator.
- No evidence of active, ongoing regrowth present at baseline.
- Patients with alopecia totalis/universalis can be included as long as the current episode of hair loss meets the criteria of up to 50% total hair loss (i.e. they may have had a

previous episode of AT or AU which demonstrated regrowth of hair, and they are not currently AT or AU), and as long

- Patients with more than 50% total scalp hair loss at baseline can be included as long as the specified area to be treated is limited to less than 50% of total scalp area

Exclusion criteria

- Patients with a history of or existing skin diseases affecting the scalp such as psoriasis or seborrheic dermatitis and patients with evidence of infection or skin cancer in the treated areas
- Patients in whom the diagnosis of alopecia areata is questionable
- Patients in whom regrowth is present/evident at baseline in the areas to be treated
- Patients with active medical conditions or malignancies (except adequately treated basal or squamous cell carcinoma of the skin) which in the opinion of the investigator would increase the risks associated with study participation, including patients with a history of recurrent infections
- Women of childbearing potential who are unable or unwilling to use two forms of birth control for the study duration or women who are pregnant or nursing
- Patients known to be HIV or hepatitis B or C positive or otherwise immunocompromised
- Patients with evidence of adrenal cortex abnormality or previous significant adverse reaction to intralesional steroids
- Patients unwilling or unable to discontinue treatments known to affect hair regrowth in alopecia areata
- Patients who have been treated with intralesional steroids, systemic steroids, anthralin, squaric acid, DPCP (diphenylcycloprophenone), protopic, minoxidil or other medication which in the opinion of the investigator may affect hair regrowth, within one month of the baseline visit.

Study procedures

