Screening: A complete medical history will be taken. Patients will be specifically asked about renal, hepatic or adrenal abnormalities and pregnancy (women of child bearing potential only). In keeping with current standard of care, no routine blood work will be done, unless it is deemed necessary by the investigator. Patients will be randomly assigned to IL TAC 2.5mg/ml, IL TAC 5mg/ml or IL TAC 10mg/ml or intralesional saline in a 1:1:1:1 ratio based on a computer generated randomization list. The list will be generated prior to study initiation. Based on the randomization list, patients will be assigned to treatment vs. placebo based on the order in which they are enrolled. The assignment will be made by study personnel not involved in making clinical assessments or evaluations. The patient and the assessing physicians will remain blinded to the treatment assignment for the duration of the study. Baseline assessments of disease severity will be done, including SALT, Physician global assessment (PGA), patient global assessment and patient quality of life assessment. Patients will have study medication injected once per month by the study physician in accordance with current standard of care clinical practice. Per current clinical practice, attempts will be made to treat all areas of hair loss due to AA, however (also in accordance with current standard of care in clinical practice) the dose of intralesional triamcinolone injected will be limited to a maximum of 30mg per month(16, 4). Therefore, patients being

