Power analysis is based on a chi-squared test of proportions of responders in the 4 study groups, where response is defined as 50% reduction in SALT score. Effect size is quantified in terms of Cohen's w , a function of the response rates in the fourgroups (15). A minimal treatment effect size of 40% (Cohen's $w = 0.4$) i.e. a 50% response rate for active drug (IL TAC 2.5mg/ml, 5mg/ml or 10mg/ml) versus a presumed spontaneous remission response rate of 10% for patients receiving inactive IL saline, would be considered clinically meaningful in this study. To achieve 80% power to detect the desired effect size of 40% with a usual 5% level of significance (alpha), we would require approximately 17 subjects per arm (68 subjects in total). With this sample size, an effect size of 50% (Cohen's $w = 0.5$, "large" effect) would ensure approximately 95% power. Our postulated effect size for IL TAC is based on impressions due to clinical use of IL TAC in AA, however an explicit aim of this pilot study is to objectively and more precisely quantify the actual treatment effect of the various doses of IL TAC versus saline placebo.

Data Analysis Plan

The primary analysis will be a comparison of response rates in the 4 study groups, using a chi-squared test of proportions. If the 4-group comparison is significant, we will compare the efficacy and safety profiles of the three doses of intralesional triamcinolone head to head. For secondary outcomes that are binary (response/non-response), we will follow the same strategy. For secondary outcomes that are continuous (e.g. change in SALT measurement or PGA), we will conduct 4-group ANOVA tests, followed by pairwise

comparisons, if necessary. In both cases, Bonferroni correction will be made to adjust for multiple testing. To assess safety, we will summarize and test the incidence rates of adverse events across groups.

If possible, we will attempt to stratify the patients based on baseline degree of hair loss e.g. 0-25% vs. 26-50% hair loss in order to assess if response is correlated with degree of hair loss present at baseline. (Olsen E. Investigative guidelines for alopecia areata.

Dermatologic therapy 24, 2011 311-319

All outcomes will be analyzed on the intent to treat (ITT) basis.

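### The population is called recent-onset but eligibility sets no upper limit on duration, and duration, which the eligibility proviso links to regrowth, is used in no analysis; the cost is precision, not validity

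*Combined protocol and SAP*

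**What the plan says.** Three parts of the combined protocol and SAP bear on this point.

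- **Population.** Human Subjects Involvement, Characteristics, and Design describes "68 patients with a diagnosis of patchy AA of recent onset (duration of at least 3 months"). Its only number is a minimum. The same sentence adds that patients must "have met all inclusion and exclusion criteria".
- **Eligibility.** Inclusion criteria allow "Duration of hair loss greater than 3 months without an upper limit of duration". A proviso attached to this leaves the matter to clinical judgement: "as long as there is reason to believe that regrowth is possible in the opinion of the investigator". The lower bound here excludes exactly 3 months; the one in the population description includes it. Neither place says whether duration refers to the current episode or to the disease overall.
- **Allocation and analysis.** Under Study procedures (Screening), allocation follows a computer-generated 1:1:1:1 list: "patients will be assigned to treatment vs. placebo based on the order in which they are enrolled". No stratification factor is named. In the Data Analysis Plan, "The primary analysis will be a comparison of response rates in the 4 study groups, using a chi-squared test of proportions". Continuous secondary outcomes use four-group ANOVA, and relapse uses chi-squared, Kaplan-Meier and log-rank methods. The one baseline factor mentioned is extent of loss: "If possible, we will attempt to stratify the patients based on baseline degree of hair loss". Duration appears in none of these analyses.

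**The concern.** A minimum duration cannot define recent onset, so the population description and the criterion describe different patients. Someone with many years of hair loss could be enrolled under the criterion, given a favourable opinion from the investigator, and would still fall outside the description.

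The criterion also ties duration to outcome. It leaves duration unlimited only where regrowth is thought possible, which makes sense only if duration is believed to affect regrowth. The mix of durations then depends on investigator judgement at two sites (38 and 30 patients planned, under Recruitment). With 17 per arm and no stratification, long-standing cases can fall unevenly across the arms by chance, and the plan has no means of adjusting for that. The protocol states that it aims to quantify the effect of each dose precisely, so precision given up at almost no saving deserves attention.

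**Working it through.** **1. The plan's own figure.** The Sample size section gives 68 patients (17 per arm) for 80% power at Cohen's w = 0.4 and alpha 0.05. For a 3-df chi-squared test the noncentrality is N × w² = 68 × 0.16 = 10.88, which gives power 0.799. The figure reproduces. It contains no duration input, so this point does not alter it.

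**2. Which text governs.** The population sentence requires all listed criteria to be met, so the open-ended criterion decides who enters. The recent-onset label is a misdescription and not a second eligibility rule.

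**3. Validity of the unadjusted test.** Under a null in which half the patients respond at 50% and half at 20% in every arm (assumed rates), the simulated type I error of the four-group chi-squared test is 0.048. Leaving duration out does not inflate it.

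**4. Chance imbalance (illustration).** Assume half of patients have long-standing disease, so each arm's count is Binomial(17, 0.5).

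| Comparison | Chance of a gap of 5 or more such patients |
|---|---|
| One given pair of arms | 12% |
| Largest minus smallest of the three active arms | 27% |

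Suppose also that long-standing patients respond to active drug at 20% to 30%, against 50% in the rest. Two active arms that differ by 5 such patients then differ in expected response by 5/17 × (0.50 − 0.30) = 5.9 points to 5/17 × (0.50 − 0.20) = 8.8 points, with no dose effect at all. The share and the rates are assumptions; the documents give neither.

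**5. What adjustment gains for a continuous outcome.** Let ρ be the within-arm correlation of log duration with the outcome. There are 68 − 4 = 64 within-arm degrees of freedom. With one roughly normal covariate and a common slope, the expected variance of an arm contrast, relative to ANOVA, is

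(1 − ρ²) × (1 + 1/(64 − 2)) = (1 − ρ²) × 63/62.

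| ρ (assumed) | Relative variance | Change |
|---|---|---|
| 0.1 | 0.99 × 1.0161 = 1.006 | +0.6% |
| 0.2 | 0.96 × 1.0161 = 0.975 | −2.5% |
| 0.3 | 0.91 × 1.0161 = 0.925 | −7.5% |
| 0.4 | 0.84 × 1.0161 = 0.854 | −14.6% |

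Break-even is at 1 − ρ² = 62/63, that is ρ² = 1/63 and ρ ≈ 0.13. These figures assume all 68 patients contribute data.

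**6. Events for a supportive logistic model.** At the planning rates, expected responders are 17 × (0.10 + 0.50 + 0.50 + 0.50) = 27.2. That is few, but enough for three arm terms and one covariate in a model labelled supportive.

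**The case against.** The strongest reply is that this is one stray phrase. The specific aims give the population as mild to moderate patch-type disease with no duration limit, and the listed criteria are checked at screening and baseline. That stands. A reader might infer that the trial's conclusions would be stated for recent-onset disease, or that the two sites would enrol under different rules; the documents support neither.

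A second reply is that the link to regrowth rests only on the investigator proviso, with no direction, size or cut-off, and that the proviso already handles duration in part at entry. That also stands, and it is why any gain is conditional.

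A reader might go further and infer a large loss of power by assuming that long-standing patients respond less often. Such a loss comes wholly from the lower assumed mean response. It would arise whatever the population is called, and a covariate would not restore it, so it does not measure this defect. Nor should imbalance be quoted across all four arms in the illustration above: saline response there is held at 10% whatever the duration, so imbalance in that arm would change nothing.

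Finally, it can be said that adding a covariate in a self-described pilot is a matter of preference. For the primary test that is fair, and no change to it is proposed. For the continuous outcomes, duration has to be ascertained for eligibility anyway, and adding it after unblinding would be open to the charge of being data-driven.

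**Conclusion.** The point holds in a limited form. The population description and the duration criterion conflict, on the recent-onset label and on the lower bound, and must be reconciled. Separately, the analysis plan leaves out a baseline variable that the protocol itself implies is related to regrowth.

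The consequence is in precision and protection against chance imbalance. A reader might infer bias or an inflated type I error, but randomisation rules that out. For continuous outcomes, adjustment would reduce the variance of an arm contrast by about 2% to 15% if the correlation is 0.2 to 0.4, and would cost under 1% if it is 0.1. The correlation is an assumption, and the documents give no size for the effect. Reconciling the wording would not by itself change any result; pre-specifying the covariate could.

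**What to change.** 1. Reconcile the population description with the duration criterion, in whichever direction the sponsor intends. Use one lower bound, and say whether duration means the current episode.
2. Record duration of the current episode as a baseline variable and report it by arm.
3. In the Data Analysis Plan, pre-specify log duration as a covariate for the continuous outcomes (ANCOVA in place of ANOVA), keeping the planned pairwise comparisons and Bonferroni correction.
4. Add one supportive logistic model of week-24 response with arm and log duration. Leave the primary chi-squared test unchanged.

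The cost is some protocol wording, one baseline field drawn from information already needed for eligibility, and one degree of freedom per model. The gain appears only if duration is in fact prognostic, beyond a correlation of about 0.13. The logistic model rests on about 27 expected responders, of whom only 17 × 0.10 = 1.7 are expected on saline, so its estimates will be imprecise and should be presented as supportive only.

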Each year the Dermatology Department at CUMC sees 600 AA visits each year. Of these we expect roughly 20 to 30% to be eligible for this study of mild to moderate patch type alopecia. We also have a database of almost 400 patients evaluated at CUMC as part of the alopecia areata registry who have expressed an interest in being contacted for clinical trials in alopecia areata. In addition, we hope to have information regarding the study posted on the website for the National Alopecia Areata Foundation (NAAF) the largest AA patient advocacy organization. We expect to complete accrual of 68 patients within the 1 to 2 year study period (38 patients at CUMC and 30 at the University of Minnesota). This time frame will enable 6 months on treatment and 6 months follow-up off drug (for patients who qualify) and completion of the clinical correlative portion of the study

Assessment of Safety

Safety precautions such as the use of highly experienced investigators, frequent visits, and close monitoring of clinical and laboratory findings have been implemented in the protocol and are specified in the Schedule of Assessments. Hematology and chemistry measurements, including WBC count, platelet and absolute neutrophil counts, urinalysis and hepatic panel may be obtained at screening and at other time points if deemed necessary by the investigator.

All physical examination findings, vital sign abnormalities, and clinical laboratory abnormalities, will be captured as AEs when deemed medically significant by the investigator. A qualified physician associated with the study will be available to assess clinical signs and symptoms that may be indicative of an adverse event. Safety will be assessed by

summarizing the incidence and type of AEs. The proportion of patients who discontinued treatment will be summarized.

Methods and Timing of Safety Assessments

Adverse Event Reporting

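### One enrolment-order list for two sites, with no stated blocking or stratification, and a primary test that ignores site and baseline SALT: no bias, but avoidable loss of precision and harder-to-read dose and severity comparisons

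*Combined protocol and SAP*

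**What the plan says.** Under Study procedures (Screening), allocation is "in a 1:1:1:1 ratio based on a computer generated randomization list". The text continues: "The list will be generated prior to study initiation", and "patients will be assigned to treatment vs. placebo based on the order in which they are enrolled". Staff who make no clinical assessments do the assigning. The Human Subjects section also speaks of a single list. No section gives a block size, strata or separate site lists.

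Recruitment plans "38 patients at CUMC and 30 at the University of Minnesota". Sample size asks for "approximately 17 subjects per arm (68 subjects in total".

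The Data Analysis Plan makes the primary analysis a chi-squared comparison of response rates in four groups, with no covariates. If it is significant, the three doses are compared head to head. Severity enters only afterwards and conditionally: "If possible, we will attempt to stratify the patients based on baseline degree of hair loss", with 0-25% and 26-50% as example bands and the stated purpose of seeing whether response relates to baseline loss. The inclusion criteria also admit patients above 50% loss if the treated area is limited, so some patients may fall outside both bands. SALT is measured at screening.

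**The concern.** Baseline extent could plausibly affect response here. The endpoint is percent change in whole-scalp SALT, while treatment is limited to 30 mg a month, which the protocol turns into maximum volumes of 12, 6 and 3 ml for the three strengths. Site could matter too, because SALT is an estimated percentage and the investigator chooses the injection areas.

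If either factor is prognostic, four arms of 17 from an unstratified list will often differ in its mix, and the planned test makes no allowance for that. What is at stake is how cleanly the doses can be compared, how readable the severity analysis is, and some precision in a study whose declared aim is to quantify the effect of each dose.

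**Working it through.** **1. The plan's own figure.** For a chi-squared test with 3 df, alpha 0.05 and 80% power, the noncentrality is 10.90. N = 10.90 / 0.4² = 68.1, so 68 reproduces. Power at N = 68 is 79.9% for w = 0.4 and 94.8% for w = 0.5, as stated. (Rates of 10/50/50/50% correspond to w = 0.354, which is a separate matter. The baselines in step 5 are simulated at those rates, so they differ from 80%.)

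**2. Chance imbalance.** Inputs: 17 per arm; site 38/30 (Recruitment); severity split not given, so 34/34 and 20/48 are assumed. If K of 68 patients carry a characteristic, the chance that the arms hold a, b, c, d of them is C(17,a)·C(17,b)·C(17,c)·C(17,d) / C(68,K). Four patients are 4/17 = 24 points; six are 6/17 = 35 points.

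| Split | Any of six pairs, 4 or more | Any of six pairs, 6 or more | One named pair, 4 or more | One named pair, 6 or more | Placebo vs pooled active, 20 points or more |
|---|---|---|---|---|---|
| Site 38/30 | 62% | 23% | 23% | 6% | 9% |
| Severity 34/34 | 63% | 23.5% | 23% | 6% | 9% |
| Severity 20/48 (or 48/20) | 56% | 16% | 19% | 4% | 12% |

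The last column depends on the threshold, because placebo counts move in steps. At 15 points it is 26% for 34/34 and 36% for 20/48.

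**3. What an imbalance does to a contrast.** Shift = imbalance × difference in response between bands. With an assumed difference of 10-30 points, a 20-point imbalance shifts a contrast by 0.20 × 10 to 0.20 × 30 = 2-6 points, and a 30-point imbalance by 3-9 points. The standard error for 10% vs 50% is √(0.1×0.9/17 + 0.5×0.5/17) = 14 points.

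**4. Stratified list.** With permuted blocks within site × SALT band (four strata), the chance of a 20-point gap between any two arms falls to about 0% with blocks of 4 and at most 0.2% with blocks of 8. The median largest gap falls from 23.5 points to about 6-8. Arm sizes run about 15-19 with blocks of 4 and 14-20 with blocks of 8.

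**5. Primary test, by simulation.** Severity is split 34/34. In the 10/50/50/50% rows the severity effect in the placebo arm is capped at 20 points.

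| Response rates | Severity effect | Planned test, unstratified list | CMH by SALT band, stratified list |
|---|---|---|---|
| 10/50/50/50% | none | 76% | 75% |
| 10/50/50/50% | 30 points | 76% | 80% |
| 10/50/50/50% | 40 points | 76% | 82% |
| 20/60/60/60% | 40 points | 70% | 80% |

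Type I error (all arms at 30%) is about 5% for the planned test on an unstratified list and 4.5-4.8% for CMH on a stratified list. The unadjusted test on a stratified list becomes conservative: 3.3% and 2.1% at severity effects of 30 and 40 points. Stratifying the list while keeping the unadjusted test adds no power (74-76% in the 10/50/50/50% rows).

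**The case against.** The strongest case against is that this is a preference, not an error. The test is valid as planned, the study calls itself a pilot, and a shift of 2-6 points is small beside a standard error of 14 and a 40-point target. That stands, and it is why the point is an improvement and not a defect in the primary inference.

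Some stronger readings are tempting but unsupported:

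- A reader might infer that a sizeable imbalance is likely in the comparison that matters. The 56-63% is the worst of six pairs. For one named pair it is about one in five, and for placebo against pooled active about one in ten at 20 points.
- A reader might infer that the severity analysis will have nearly empty cells. At 34/34, some arm-by-band cell has 3 or fewer patients in only 2% of trials. At 20/48 it is 64%, but perfect balance would still leave 20/4 = 5 per small cell. The sparsity comes mainly from N = 68.
- A reader might infer that different evaluators rate SALT at each site, or that severity is known to predict response. Neither is stated. The plan proposes the severity analysis in order to find out.
- A reader might infer simple randomisation. In that case some arm would have 12 or fewer patients in 38% of trials, but the documents do not say so. The silence on blocking is a gap in description.

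The remedy also has costs. A block of 4 holds each arm once, so unblinded staff who prepare or inject could deduce the last assignment in a block. Changing the test means restating the power basis.

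**Conclusion.** The point holds as a recommended improvement. Allocation is described as one list in enrolment order, with no stated blocks or strata, and the primary test ignores two factors known before assignment. There is no bias and no inflation of type I error. The cost is in precision and in interpreting the dose and by-severity comparisons.

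The site figures use the planned 38/30 accrual. The severity figures rest on assumed splits of 30:70 to 50:50. The power gain rests on an assumed 30-40 point severity effect: about 3-6 points at the plan's own response rates, and up to about 10 at 20/60/60/60%. That the list is single and unstratified rests on the singular wording and on the absence of any other description.

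**What to change.** - **List.** State the scheme in Study procedures. Use permuted blocks with concealed, varying sizes (for example 4 and 8), stratified by site and screening SALT (25 or less vs more than 25), with patients above 50% in the upper stratum.
- **Analysis.** Make the primary four-group comparison a CMH general-association test stratified at least by SALT band. Prefer it to a logistic model, because few placebo responders are expected (10% of 17 is fewer than 2). Restate the power basis for that test. The list and the test should change together, since the unadjusted test is conservative after stratified allocation.

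**Cost.** No extra patients and no new measurements. Assignment must be coordinated across four short lists, arms may drift from 17 to about 14-20, and power falls by about 1-2 points if severity does not predict response.
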